Our hypothesis is that patients, who are classified as frail, will have increased risk of deterioration in global QoL and physical functioning (PF), assessed by the corresponding EORTC QLQ-C30 scales ranging from 0-100. A difference of 10 points on these scales is considered a clinically significant difference.⁷⁶ Based on the reported prevalence of frailty in studies of other cohorts of older patients with cancer,^{18,43} one may assume that about 40% will be frail and 60% non-frail. To detect a difference of 10 points in global QoL and PF between the two groups at 8 weeks follow up, standard deviation (SD) = 30 (a conservative estimate), power 80% and significance level 5%, 119 patients will be needed in the frail group and 178 patients in the non-frail group, in total 297 patients. To document a difference of 11 points, 247 patients are needed. Based on these estimates, and taking into account that some drop out will occur, we find that including 325 patients will be satisfactory.

Strategy for the analyses

Adverse events are defined as described under Study aims, page 7-8. The patients will be classified as frail or non-frail based on GA at baseline. Primary and secondary outcomes will be compared between the non-frail and frail using bivariate regression analyses. Since the study cohort will be heterogeneous and several factors most likely will affect the outcomes, we will also estimate multivariate regression models, adjusted for these factors. The most important factors will be type of cancer, stage of disease, gender and radiotherapy regimen. Time trend models will be estimated in order to assess the development in the primary outcomes for non-frail/frail patients during the follow up period. We will also estimate bi- and multivariate regression models to assess the impact of each individual factor in GA (i.e. comorbidity, physical function, nutritional status) on the defined outcomes. Furthermore, we will use descriptive statistics to compare sociodemographic and medical data and GA findings between patients experiencing and not experiencing adverse events.

The sensitivity and specificity of EFS in identifying frail patients will be tested against the full GA. EFS ability to predict adverse events on the defined outcomes will be assessed with uni- and multivariate regression analysis, controlled for relevant co-variates (e.g. type of cancer, stage of disease, and radiotherapy regimen).

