The second secondary aim of our study is to “*Validate the Edmonton Frail Scale (EFS) as a screening instrument to identify frail patients and patients at risk of adverse events*” (see page 8).

The plan for the analyses was: “*The sensitivity and specificity of EFS in identifying frail patients will be tested against the full GA. EFS’ ability to predict adverse events on the defined outcomes will be assessed with uni- and multivariable regression analyses, controlled for relevant co-variates (e.g. type of cancer, stage of disease, and radiotherapy regimen*” (see page 17)

Partly based on the considerations stated under point 1, we have now decided to perform the validation by investigating the association between the instrument’s scores and OS in addition to association with GA findings. Another strong argument for this is that other well-known and widely used frailty screening instruments, e.g. the G8, have been widely tested against patients’ survival.¹⁻⁵ Thus, for comparison, which is important, we will do likewise.

Before embarking on these analyses, a detailed plan has also been prepared (**Appendix 2**).

3. We have decided not to use the term “frailty” when classifying the patients according to GA. Hence, we will not define the patients as frail or non-frail, but instead classify them according to their number of identified GA impairments.

Our primary hypothesis (page 8) has been revised accordingly, now reading: “*Our hypothesis is that increasing number of GA impairments is associated with increased risk of adverse events as defined, regardless of cancer type, stage, and radiotherapy procedure (localisation, dose, field size)*

This hypothesis and the primary aim of our study will be addressed in paper 3, for which a detailed plan for the analyses has also been prepared (**Appendix 3**)

This amendment also affects paper 2 as the sensitivity and specificity of Edmonton Frail Scale will be evaluated against number of geriatric deficits, not against a classification of frail vs. non-frail patients.

Explanation:

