- B) The survival of older patients with cancer referred for curative or palliative radiotherapy differ between the groups defined by formerly used/suggested cut-off points

Methods

- A) Cox proportional hazards regression model will be estimated
- B) Receiver Operating Characteristics curve analysis, Akaike's Information Criterion

Part II: Evaluate the concurrent validity of the EFS in a cohort of patients receiving radiotherapy

The aims are to

- A) describe the number and type of GA deficits within each of the formerly proposed categories of EFS (see above)
- B) assess the association between the formerly proposed EFS categories and number of GA deficits, and explore the data to find the cut-off point of EFS score that is most relevant to use in a screening procedure to ensure that the majority of patients in need of a full geriatric assessment are captured

Hypotheses

- A) the number of GA deficits increases according to the formerly proposed EFS categories (fit, vulnerable, mild frailty, moderate frailty and severe frailty) with patients with moderate/severe frailty having the highest number of GA deficits
- B) there is a significant association between EFS categories and number of GA deficits, and the proposed cut point EFS ≥ 6 for frailty is the appropriate cut-off point to ensure that a full GA is applied in patients where this is needed (based on number of GA deficits)

Methods

- A) Descriptive statistics
- B) ANOVA

Baseline data for EFS scores and the geriatric assessment will be used.

Appendix 3

Dated 18-05-21

Plan for analyses, paper no.3

Preliminary title:

Is the presence of geriatric impairments associated with quality of life and physical function after radiotherapy in older cancer patients? - A prospective observational study.

Main objectives:

In a cohort of older patients with cancer, referred for curative or palliative RT, we will:

1. assess the trend in quality of life (QoL) and physical function prior to and after RT for palliative and curative patients, and investigate if there is a significant difference in trend between the two groups
2. assess the trend in QoL and physical function prior to and after RT stratified on number of geriatric impairments present at baseline, and investigate if there is a significant difference in trend depending on the number of geriatric impairments

Predefined outcomes:

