Primary: Global quality of life (QoL) and physical function as assessed by the European Organisation for Research and Treatment of Cancer Quality of Life Questionnaire (EORTC QLQ-C30) global QoL (gQoL) and physical functioning (PF) scale.

Secondary:

- Instrumental Activities of Daily Living (ADL)-function assessed by Nottingham Extended Index of Activities of Daily Living (NEADL) based on patients' self-report.
- Role function as assessed by the EORTC QLQ-C30 role function (RF) scale
- Fatigue and pain as assessed by the EORTC QLQ-C30 corresponding symptom scales (FA = fatigue)(PA = Pain)

Exploratory: Functioning and symptom scales/items of the EORTC QLQ-C30 that are not defined as primary or secondary outcomes will be assessed for explorative purposes

Hypotheses:

1. Patients referred for palliative RT have poorer scores for all primary and secondary outcomes prior to and after RT compared to patients referred for curative treatment
2. There is a significant difference in trend in outcomes for palliative and curative patients:
 - a. patients referred for palliative RT will experience an improvement in the primary outcomes global QoL and PF, and the secondary outcomes RF, NEADL and pain (PA) within 8 weeks after RT.
 - b. patients referred for curative RT will experience a deterioration in the primary outcomes global QoL and PF and the secondary outcomes RF, NEADL and

fatigue (FA) scores from baseline to 2 weeks after RT. Thereafter the scores will return to baseline values within 16 weeks.

3. There is a significant difference in trend in outcomes depending on number of geriatric impairments
 - a. scores for the primary outcomes global QoL and PF, and the secondary outcome RF decreases with increasing number of geriatric impairments
 - b. there is a significant association between number of geriatric impairments and the primary outcomes global QoL and PF as well as the secondary outcome RF scores

Timeline for the assessments: Patients answered EORTC QLQ-C30 and NEADL at five different time points: baseline, when completing RT (except palliative patients who received only a single fraction were per protocol test schedule not asked to answer EORTC QLQ-C30, and patients who received <10 fractions were not asked to answer NEADL), and 2, 8 and 16 weeks after RT. We will exclude the assessment of NEADL at the end of RT from our analyses because patients with short courses of RT did not fill in this questionnaire.

Statistical approach

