Categorical baseline characteristics of curative and palliative patients will be described with frequencies and percentages, while continuous with means and standard deviations (SD) or median and min-max values.

Raw scores for all QLQ-C30 scales/items will be transformed into scales ranging from 0-100 in accordance with the official manual for this questionnaire. NEADL item scores will be summarized into a scale ranging from 0-66. Missing NEADL items scores will be imputed as follows:

The missing values are assumed to be missing at random (MAR), and will be imputed if at least half of the items of the scale had been answered. The imputation will be performed by generating an empirical distribution for each item based on non-missing values, and a random number drawn from it was used to replace the missing value.

To answer Study aim 1 and test our first hypothesis, the primary outcomes, global QoL and PF will be assessed by linear mixed model with fixed effects for (non-linear) time, treatment group (curative vs. palliative) and the interaction between the two. Random effects for patients will be included. The models will be adjusted for age, gender, performances status (ECOG PS) and cancer type. The secondary outcomes RF, NEADL and pain scores will be evaluated by similar models.

To answer Study aim 2 and test our second hypothesis, similar models to those describe for aim 1 will be performed for the primary outcomes global QoL and the secondary outcome RF. However, these models will use number of geriatric impairments as a stratification variable instead of treatment intent (palliative vs curative). The models will be adjusted for age, gender, cancer type, treatment intent (curative vs palliative) and ECOG PS.

Sensitivity analyses to estimate models for non-imputed variables for NEADL will be also be performed.

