For explorative purposes linear mixed model with fixed effects for (non-linear) time, treatment group (curative vs. palliative) and the interaction between the two will be estimated to assess differences in trend between palliative and curative patients for emotional function (EF, insomnia, appetite loss). Similar models will also be estimated to assess possible differences in trend in pain, fatigue, insomnia, and appetite loss between groups defined according to number of geriatric impairments. For these models number of geriatric impairments will be used for stratification instead of treatment intent. No adjustments will be made in any of the explorative models.

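### Appendix 3 makes physical function a primary outcome of the impairment-count hypothesis but lists no impairment-count model for it

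*Combined protocol and SAP*

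**What the plan says.** Amendment 4, point 3, drops the frail/non-frail classification. The investigators will "instead classify them according to their number of identified GA impairments", and the primary hypothesis is reworded to match. The amendment then states: "This hypothesis and the primary aim of our study will be addressed in paper 3". The plan for paper 3 is Appendix 3.

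Within Appendix 3:

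- Main objective 2 is to "assess the trend in QoL and physical function prior to and after RT stratified on number of geriatric impairments present at baseline".
- The predefined primary outcomes are the global QoL and PF scales of the QLQ-C30. The secondary outcomes are NEADL, role function (RF), fatigue and pain.
- Hypothesis 3b says that "there is a significant association between number of geriatric impairments and the primary outcomes global QoL and PF", with RF added as a secondary outcome. Hypothesis 3a names the same three outcomes.
- In the statistical approach, the aim-1 models (palliative versus curative) cover global QoL and PF, and then RF, NEADL and pain.
- For aim 2 (number of impairments), "similar models to those describe for aim 1 will be performed for the primary outcomes global QoL and the secondary outcome RF".
- The exploratory models by impairment count "assess possible differences in trend in pain, fatigue, insomnia, and appetite loss between groups defined according to number of geriatric impairments".

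The main protocol names both primary outcomes in its sample-size section: "To detect a difference of 10 points in global QoL and PF between the two groups at 8 weeks follow up". Its analysis strategy adds: "Time trend models will be estimated in order to assess the development in the primary outcomes for non-frail/frail patients during the follow up period".

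**The concern.** The aim-2 sentence is where the plan says which models will test the impairment-count hypothesis. It gives one primary outcome and one secondary outcome, although the objective and hypotheses it serves name two primary outcomes. PF is not picked up by the exploratory list that follows.

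Because Amendment 4 sends the primary hypothesis to paper 3, the gap falls on the main analysis of the study. Someone checking the published paper against its plan would find no listed PF model by impairment count. Such a model could be run or left out without departing from the model text. Prespecifying a co-primary outcome is meant to remove that freedom.

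Two smaller mismatches appear in the same section:

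- Fatigue is a secondary outcome that hypotheses 1 and 2b cover, but the aim-1 secondary list omits it.
- The aim-2 models are said to test the second hypothesis. In the numbered list, that one concerns palliative versus curative patients; the impairment-count hypothesis is the third.

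**Working it through.** **Background figure.** The sample-size calculation is not in dispute, but it shows that PF was meant to be analysed by group. Inputs from the protocol: difference 10 points, SD 30, power 80%, significance level 5% (two-sided assumed), 40% frail and 60% non-frail, so the allocation ratio is k = 1.5.

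- Normal approximation: n(frail) = (1 + 1/k) × [SD × (1.960 + 0.842) / 10]² = 1.667 × 8.405² ≈ 117.7, and n(non-frail) = 1.5 × 117.7 ≈ 176.6. Rounded up, this is 118 + 177 = 295.
- Two-sample t-test: 118.5 and 177.8, rounded up to 119 + 178 = 297, the protocol's own figure.

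**Outcomes against models.** The outcomes each hypothesis in Appendix 3 names are set against the models its statistical approach lists for the grouping concerned. Hypotheses 3a and 3b name the same outcomes and are counted once. Models are matched to hypotheses by grouping variable, not by the hypothesis number printed in the text.

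| Hypothesis | Grouping | Outcomes named | Named | With a listed model | Missing |
|---|---|---|---|---|---|
| 1 | Treatment intent | Global QoL, PF, NEADL, RF, fatigue, pain | 6 | 5 | Fatigue |
| 2a | Treatment intent | Global QoL, PF, RF, NEADL, pain | 5 | 5 | None |
| 2b | Treatment intent | Global QoL, PF, RF, NEADL, fatigue | 5 | 4 | Fatigue |
| 3a/3b | Impairment count | Global QoL, PF, RF | 3 | 2 | PF |

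Named: 6 + 5 + 5 + 3 = 19. With a listed model: 5 + 5 + 4 + 2 = 16. Missing: 19 − 16 = 3.

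**Do the exploratory models fill the gaps?** By treatment intent they cover emotional function, insomnia and appetite loss, so fatigue is not among them. By impairment count they cover pain, fatigue, insomnia and appetite loss, so PF is not among them. Fatigue's only model is therefore an unadjusted exploratory one, by the other grouping. Neither list closes a gap.

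**The same count in distinct models.** Six outcomes by intent plus three by impairment count make 9 models needed. Five by intent and two by impairment count make 7 listed. Two are missing: PF by impairment count and fatigue by intent.

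**Slip or decision?** Three things point to a slip. The aim-2 sentence uses the plural for primary outcomes and then gives one. The aim-1 description in the same section names both. Amendment 4 changes the grouping variable from frailty to impairment count and nowhere withdraws PF.

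**The case against.** The strongest reply is that this is an omission rather than a conflict of intent. The aim-2 sentence does not exclude PF, and the intended model can be rebuilt from the surrounding text: the preliminary title, objective 2 and hypotheses 3a and 3b all name physical function; the aim-1 model is written out for PF; and the aim-2 covariates are given. A paper that left PF out would visibly clash with its own objective, so the room for selective reporting is narrow. Fatigue is not a primary or secondary outcome in the main protocol, and the misnumbered hypothesis is unlikely to mislead, since the same sentence refers to aim 2. The tally also depends on a counting rule: with 3a and 3b counted separately it would be 18 of 22, with 4 missing, and the single missing fatigue model is counted under two hypotheses.

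Much of this stands. The intent is recoverable, no design element is affected, and the 16-of-19 figure is a description under a stated rule; the 7-of-9 count of distinct models avoids the double counting. The reply does not remove the gap. The list of models for the primary hypothesis disagrees with the hypothesis it is meant to test, and no other sentence in Appendix 3 supplies the missing model. That a reader can infer the right list is a reason to expect an easy correction, not a reason to leave it.

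**Conclusion.** The concern holds. As written, Appendix 3 gives no impairment-count model for PF, which is 1 of the 2 primary outcomes and 1 of the 3 outcomes under hypothesis 3, in the paper that carries the study's primary hypothesis. Fatigue, 1 of 4 secondary outcomes, has no model by treatment intent, so hypotheses 1 and 2b cannot be judged for it from the listed models; this does not touch the primary hypothesis. The hypothesis numbering in the aim-2 text is wrong.

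The most likely explanation is a drafting slip, though the text does not settle that. Nothing here implies bias in an estimate, loss of power or a fault in the sample size. The conclusion rests on reading the model lists as complete, which is how a detailed prespecified plan would be read. It should be fixed because it concerns a co-primary outcome, but it is not a threat to the study.

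**What to change.** In the statistical approach of Appendix 3:

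- Aim 2: list global QoL and PF as the primary outcomes and RF as the secondary outcome, and state that these models test hypothesis 3.
- Aim 1: list RF, NEADL, fatigue and pain as the secondary outcomes, and state that these models test hypotheses 1 and 2.

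If any outcome was left out on purpose, say so and amend the objective and hypotheses to match. Date the correction, and state whether the affected analyses had already been run.

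The cost is a few words of plan text and two additional linear mixed models (PF by impairment count, fatigue by treatment intent) on data already collected. Design, data collection and sample size do not change.

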Severe loss of muscle mass may occur due to aging, but may also be a result of diseases, including cancer.^{30,51,52} In oncology settings, the phenomenon has often been referred to as sarcopenia,⁵³ whereas in geriatric medicine, there is a broad agreement that this term should be used for severe muscle loss in combination with either reduced muscle strength or reduced physical function.⁵² In older adults with non-malignant illnesses, severe loss of muscle mass is associated with frailty, physical deterioration, falls, hospital admissions and increased mortality.^{54,55} In patients with cancer, there is evidence that loss of muscle mass is common and associated with poorer survival and increased toxicity of systemic cancer treatment.^{56,57} Thus, in older patients with cancer, loss of muscle mass may have several causes, but it seems relevant to assume that assessment of muscle mass would contribute to determine the patient's vulnerability and risk of adverse treatment effects. Whether this is the case for older patients receiving EBRT has, as far as we know, not been investigated.

Loss of muscle mass may also be related to an active inflammatory response.⁵⁸ Neither the underlying mechanisms nor the correlation between clinical frailty, muscle loss and active inflammation is fully clarified.

GA in the municipal health services

GA for older cancer patients have been tested and found feasible both in larger university hospital based- and smaller oncological clinics.^{24,25} Whether such an assessment is feasible in the municipal health services is unknown.

Study aims

The overarching aim is to generate knowledge that may provide a basis for developing a targeted and feasible intervention to prevent adverse events during and after curative and palliative EBRT in patients ≥ 65 years.

Definitions: adverse events and outcomes

Adverse events are defined as reduction in QoL, physical deterioration, increased need for help in daily life activities and/or need for residential care.

Primary outcomes are global QoL and physical function as measured by the European Organization for Research and Treatment of Cancer Quality of Life Questionnaire C-30 (EORTC QLQ-C30).⁷⁹

Secondary outcomes are the ability to maintain everyday activities as measured by the Nottingham Extended Activities of Daily Living (NEADL), hospital- and nursing home admittance.

Detailed aims and hypotheses:

Primary aims and hypotheses

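### Paper 3 carries the primary adverse-event hypothesis, but its adjusted impairment-count models name only global QoL and RF: PF is missing, probably by a slip, and no appendix models NEADL or admissions by impairment count

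*Combined protocol and SAP*

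**What the plan says.** Amendment 4, point 3, drops the frail/non-frail classification and restates the primary hypothesis: "increasing number of GA impairments is associated with increased risk of adverse events as defined". It adds: "This hypothesis and the primary aim of our study will be addressed in paper 3", with Appendix 3 as the detailed plan.

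The protocol section on definitions and outcomes gives the meaning: "Adverse events are defined as reduction in QoL, physical deterioration, increased need for help in daily life activities and/or need for residential care". It names global QoL and PF (QLQ-C30 scales) as primary outcomes. The secondary outcomes are NEADL and "hospital- and nursing home admittance".

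Appendix 3 keeps global QoL and PF as primary. Objective 2 is to "assess the trend in QoL and physical function prior to and after RT stratified on number of geriatric impairments present at baseline". Hypothesis 3a says that "scores for the primary outcomes global QoL and PF, and the secondary outcome RF decreases with increasing number of geriatric impairments", and hypothesis 3b that "there is a significant association between number of geriatric impairments and the primary outcomes global QoL and PF", with role function (RF) added.

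The statistical approach for aim 2 then states that "similar models to those describe for aim 1 will be performed for the primary outcomes global QoL and the secondary outcome RF". These models are adjusted for age, gender, cancer type, treatment intent and ECOG status. The paragraph says it tests hypothesis 2, but in Appendix 3 hypothesis 2 concerns palliative versus curative trends and the impairment-count hypothesis is number 3. NEADL is modelled only under aim 1, by treatment intent. The remaining impairment-count models are exploratory and unadjusted, for pain, fatigue, insomnia and appetite loss.

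**The concern.** The hypothesis given to paper 3 is wider than the models written for it. If the aim 2 paragraph is followed as it stands, the study's main exposure is tested against global QoL but not against the other primary outcome. The paper would then not report, from an adjusted model, whether patients with more impairments lose more physical function. Nor would it say whether they come to need more help or enter residential care. Those answers are meant to show whom a later intervention should target.

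The gap also leaves room for choice. If the plan does not say whether PF, NEADL and admissions are analysed by impairment count, that can be decided after results are known.

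**Working it through.** **1. Outcomes set side by side.** The last column counts adjusted models with the number of impairments as exposure, across Appendices 1 to 3.

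| Outcome | Protocol status | In adverse-event definition | In Appendix 3 hypothesis 3 | Adjusted count model |
|---|---|---|---|---|
| Global QoL | primary | yes (QoL) | yes | yes |
| PF | primary | yes (physical deterioration) | yes | none |
| NEADL | secondary | yes (need for help) | no | none |
| Nursing home admission | secondary | yes (residential care) | no | none |
| Hospital admission | secondary | no | no | none |
| RF | secondary in Appendix 3 only | no | yes | yes |

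Appendix 1 concerns overall survival. Appendix 2 concerns the Edmonton Frail Scale against survival and GA deficits. Neither supplies a missing model. As written, 1 of 4 adverse-event components is covered; with PF restored, 2 of 4.

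**2. Are the data there?** Yes. Nursing home use is registered at each assessment point (Use of municipal health services). Hospital admissions come from hospital records and the national patient registry (Medical data; Registry data).

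**3. The plan's own sample size names PF.** The inputs, from Patient selection and sample size, are a 10-point difference in global QoL and PF at 8 weeks, SD 30, 80% power, 5% level (taken as two-sided) and a 40:60 split.

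- Formula: n(frail) = (1.960 + 0.842)² × 30² × (1 + 1/1.5) / 10² = 117.8, so 118, plus 177 non-frail, total 295.
- The t-based version gives 118.5 and 177.8, rounded up to 119 + 178 = 297, the stated figure.
- For 11 points it gives 98.07 and 147.11, rounded up to 99 + 148 = 247, also as stated.

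The calculation reproduces. PF was one of the outcomes on which the study was sized.

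**4. Scale of the omitted PF model (illustration).** Assumptions not in the documents: SD of the count 1.5 to 2, SD of PF change 20 to 30, covariate R² 0.2. The formula treats PF as a single change score, which is simpler than the planned mixed model: detectable slope = 2.802 × SD(change) / [SD(count) × √(N × 0.8)].

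- N = 301 (Appendix 1), most favourable: 2.802 × 20 / (2 × 15.52) = 1.8 points per impairment.
- N = 301, least favourable: 2.802 × 30 / (1.5 × 15.52) = 3.6 points per impairment.
- Over four impairments: 7 to 14 points.
- If 25% lack a score (N = 226): 2.1 to 4.2 per impairment, 8 to 17 over four.

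The protocol's threshold of 10 points lies inside these ranges. The four-impairment contrast is itself a choice.

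**5. Precision for admissions (illustration).** Event rates are unknown. Take a difference of 10 percentage points, N = 301 split 181 v 120 (the planning split, used only for scale) and a two-proportion test with pooled null variance. Power is 83% at 5 v 15%, 68% at 10 v 20%, 51% at 20 v 30%, 43% at 30 v 40% and 40% at 40 v 50%. It depends strongly on the event rate.

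**The case against.** **PF is only a wording slip.** PF stands in Appendix 3's working title, objective 2, primary outcomes, hypotheses 3a and 3b, and the aim 1 models that aim 2 copies. The aim 2 sentence uses the plural for primary outcomes and then names one. This is persuasive. A reader might infer that PF was deliberately dropped; the documents do not support that. But the contradiction is in the one sentence that specifies the model, so it still needs correcting.

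**NEADL by count is a legitimate scope choice.** Hypothesis 3 does not mention NEADL, and Appendix 1 lists NEADL as a GA component, so regressing it on a count that contains it is partly circular. Both points stand. Leaving NEADL out agrees with hypothesis 3, but not with the wider hypothesis that Amendment 4 gave to paper 3.

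**Admissions are covered elsewhere.** Strategy for the analyses plans regressions of all primary and secondary outcomes, and Amendment 4 describes its list of papers as what is planned so far. However, those regressions compare frail with non-frail patients, a split Amendment 4 abandoned, and no passage transfers them to the count. The further papers named concern MoCA and feasibility. Amendment 4 openly announces the loss of the CT muscle analysis but no removal of admissions. The fair complaint is that the plan does not say where they will be analysed. Hospital admission is weaker ground than nursing home admission, because it is a secondary outcome outside the adverse-event definition.

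**Trend models already test deterioration.** For the scores they include, they do: the time-by-count interaction tests differential mean decline, in line with how the protocol frames deterioration. A reader might infer that score trends cannot address the hypothesis at all, or that deaths and unreturned forms bias them. Neither inference is part of this point.

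**Conclusion.** The point holds as an inconsistency between the hypothesis assigned to paper 3 and the models written for it. It should be corrected, but it does not undermine the design.

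The firm part is textual and needs no assumption. The adjusted aim 2 models omit PF, against objective 2 and hypotheses 3a and 3b, and the paragraph cites the wrong hypothesis. NEADL, nursing home admission and hospital admission have no impairment-count model in any appendix. Literally read, that leaves one of two primary outcomes and three of four adverse-event components without an adjusted test of the main exposure. If PF is a slip, two of four components remain untested.

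The numerical illustrations rest on assumed SDs, R² and event rates. They suggest that a PF model could be informative near 10 points. They do not support a general statement that admission analyses would be underpowered, which a reader might infer from the higher event rates alone.

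**What to change.** 1. In the aim 2 paragraph of Appendix 3, name PF with global QoL and RF in the adjusted mixed models, and refer to hypothesis 3. The models are otherwise unchanged.

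2. Then choose one of two courses.
   - **Add supportive analyses by impairment count.** For NEADL, use a count without the NEADL-based IADL item, if the count includes one. For admissions, count from the end of radiotherapy to 16 weeks after it, because time from baseline to the last assessment varies with treatment length (Follow up). For nursing home admission, restrict to patients not already resident in a nursing home at the end of radiotherapy. For hospital admission, count new admissions only. Use few covariates or penalisation if events are few, and show deaths without admission separately.
   - **Or narrow the claim.** State that paper 3 tests score trends in global QoL, PF and RF, not the full adverse-event hypothesis, and say where admissions will be analysed.

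Cost: wording changes, one more outcome in an existing model family and, under the first course, one NEADL model and two regressions on data already planned for collection. The downside is a few more reported outcomes. Precision for admissions depends on unknown event rates, so those results are supportive and should be read through their confidence intervals.
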